12.4 Protocol Deviations

It is the investigator's responsibility to ensure that there are no deviations from the protocol except in cases of medical emergencies, when the deviation is necessary to protect the life or physical well-being of the participant. In the event of any deviation from the protocol, a Protocol Deviation Form will be completed. The occurrence of protocol deviations will be monitored by the sponsor for evaluation of investigator compliance to the protocol, Good Clinical Practice (GCP), and regulatory requirements. The investigator will inform the EC of protocol deviations according to requirements of each reviewing EC.

A protocol deviation for this protocol consists of, but is not limited to, the following:

- Failure to obtain participant's informed consent prior to any study-related activities and the index procedure
- Enrollment of participants who do not meet all eligibility requirements
- Failure to conduct protocol required clinical follow-ups and within time windows
- Failure to report SAEs according to protocol requirements

In the event of any deviation from the protocol, the investigator will be notified of the site's non-compliance. Corrective actions will be advised if necessary and the methods, plan or other activities put in place to ensure non-recurrence will be documented by the investigator and forwarded to the sponsor or their designee. Continued protocol deviations despite re-education of study site personnel and/or persistent protocol deviations may result in termination of the site's study participation. Participants already enrolled at these sites will continue to be followed per protocol guidelines.

12.5 Termination of Study Site Participation

The sponsor reserves the right to stop study enrollment at a study center at any time during the study. Specific instances that may precipitate terminating a study center may include the following:

- Unsatisfactory participant enrollment
- Failure to comply with protocol
- Failure to obtain informed consent
- Inaccurate and/or incomplete data recording on a recurrent basis
- Failure to report SAEs in timely manner on a recurrent basis
- Loss of (or unaccounted for) investigational product inventory
- Severe protocol deviations without justification or failure to implement corrective actions

13 DATA HANDLING AND RECORD KEEPING

For the study duration, the investigator will maintain complete and accurate documentation including but not limited to the following: medical records, study progress records, laboratory reports, CGM data, case report forms, signed informed consent forms, device records, and correspondence with the EC and study monitor/sponsor, AE reports, and information regarding participant discontinuation or study completion.

13.1 Source Documentation

For the duration of the study, the investigator shall take responsibility for maintaining complete and accurate source documentation.

The following materials should be included in the patient record:

- Participant medical history/physical condition prior to study involvement
- Dated and signed notes on the day of entry into the study referencing the study, the sponsor, participant study ID number, and a statement confirming informed consent
- Dated and signed notes from each participant's visit (for specific results of procedures and exams)
- AEs reported and their outcome including supporting documents
- Participant's condition upon study completion or withdrawal

13.2 Case Report Form Completion

Data will be collected primarily using the electronic case report forms (eCRF). Laboratory data and CGM data may be collected separately and integrated into the data analysis.

Primary data collection will be performed by site staff trained on the protocol and eCRF completion. All data fields will be completed where appropriate. However, if data are not available (i.e., missed visit, etc.), the site will receive instruction regarding electronic documentation. As data are entered, automated cross-check programs will search for any data discrepancies in the eCRFs. Appropriate error messages will be generated, allowing for the modification and/or verification of the entered data. Queries will generally be sent to the investigational site using an electronic data query system that includes an automated audit trail of the corrections. The investigator, or designee, will certify that the data are complete and accurate by applying an electronic signature to the eCRF. Any subsequent alterations, corrections, or additions will be reviewed and electronically signed by the investigator prior to the database lock.

The sponsor or designee will provide clinical monitoring to include eCRF review and parity checks with the source documentation, including operator worksheets retained with eCRF documentation and health care facility charts.

13.3 Record Retention

The investigator/site will maintain all records pertaining to this study for the later of (a) ten years following study completion, or (b) ten years after the study has been terminated by the sponsor, or (c) as otherwise instructed by the sponsor. Investigator will be notified by sponsor of the date of completion or discontinuation of the study.

To comply with these requirements, the investigator will not dispose of or transfer any records relevant to this study without either (1) written permission from the sponsor, or (2) providing an opportunity for the sponsor to archive the records with an external vendor.

14 ETHICAL CONSIDERATIONS

14.1 Ethic Committee Review

EC approval for the protocol and informed consent form will be obtained by the investigator prior to study participation by participants. The approval letter must be obtained prior to beginning this study and a copy must be provided to the sponsor. No changes will be made to the protocol or informed consent form without appropriate approval from the EC, the sponsor and/or the regulatory agencies. Additionally, the Principal investigator or representative will provide an EC membership list or assurance number to the sponsor or its designee.

As per oversight EC requirements, the investigator will report study progress until it is completed. Further, any protocol amendments as well as associated informed consent changes will be submitted to the EC and written approval must be obtained prior to implementation.

14.2 Informed Consent

Written informed consent must be obtained prior to any study-related activities and the index procedure.

The investigator should clearly explain that this is an elective procedure and should discuss the potential risks and benefits associated with participation in this study.

Participants providing informed consent agree to permit the sponsor or designee access to pertinent information in their medical records and other study related data concerning their participation in this study. This confidential patient information may be shared with regulatory agencies as required; however, the sponsor undertakes not to otherwise release the participant's personal and private health information.

14.3 Confidentiality

The identity of participants enrolled in the study and the information contained in their study records will be kept confidential by the sponsor. As part of the investigator training session, investigators will be instructed in the importance of confidentiality and the techniques for protecting participant's privacy and rights. Participant's personal information will be handled at all times in accordance with appropriate confidentiality standards and applicable data protection and local privacy laws.

Each participant will be assigned a study identification number to be used on eCRFs and other study records sent to the sponsor or its designee. Initials will also be used to track study participants.

Confidentiality will be protected as much as possible throughout the study. Medical records will be reviewed by representatives of the sponsor and/or its designee and will be made available for review as required by the EC and regulatory authorities. Results of data collected will be reported as statistical information only. The participant's name will not be used or otherwise disclosed unless required by law or regulation.

15 INVESTIGATIONAL DEVICE MANAGEMENT

15.1 Device Accountability

The sponsor will only distribute investigational devices to sites that are part of the clinical investigation. The sponsor will maintain complete, current and accurate records pertaining to the distribution of the investigational devices and follow record keeping requirements in accordance with Good Clinical Practices and local regulations.

The investigator is responsible for maintenance of adequate records of the receipt, disposition, and/or return of all investigational devices distributed to their site. At study termination, or termination of the site from participation in the study the sponsor will provide specific instructions to the study sites on unused investigational devices.

Use of the investigational device outside of the protocol (e.g., compassionate use) without prior written approval is strictly forbidden and may constitute grounds for removal of the investigator/site from the study.

15.2 Device Return

All unused investigational devices, including those unused due to malfunction, device failure, device complaint or device dropped on the floor, must be returned to the sponsor or its designee immediately according to the returned goods process. All devices and/or remaining components that are associated with a device malfunction or clinical procedural failure should be returned to the sponsor.

APPENDIX 1. DEFINITIONS

The Los Angeles Classification of esophagitis¹¹

- Grade A: One (or more) mucosal break no longer than 5 mm that does not extend between the tops of two mucosal folds
- Grade B: One (or more) mucosal break more than 5 mm long that does not extend between the tops of two mucosal folds
- Grade C: One (or more) mucosal break that is continuous between the tops of two or more mucosal folds but which involve less than 75% of the circumference
- Grade D: One (or more) mucosal break which involves at least 75% of the esophageal circumference

Hypoglycemia (ADA 2020)

- Level 1 hypoglycemia is a glucose concentration 54–70 mg/dL (3.0–3.9 mmol/L).
- Level 2 hypoglycemia is a blood glucose concentration <54 mg/dL (3.0 mmol/L), which is typically the threshold for neuroglycopenic symptoms.
- Level 3 hypoglycemia is a clinical event characterized by altered mental and/or physical functioning that requires assistance from another person for recovery

Severe hypoglycemia: Level 3 hypoglycemia per ADA 2020 definition.

Documented symptomatic hypoglycemia: An episode during which typical symptoms of hypoglycemia are accompanied by a measured plasma glucose concentration ≤ 3.9 mmol/L (70 mg/dL).

Probable symptomatic hypoglycemia: An episode during which symptoms of hypoglycemia are not accompanied by a plasma glucose determination but that was presumably caused by a plasma glucose concentration ≤ 3.9 mmol/L (70 mg/dL).

APPENDIX 2. SCHEDULE OF ACTIVITIES

	Screening															Week 48					
		Baseline ^[1]		Index Procedure	Week 1	Week 2	Week 4	Week 8	Week 12	Week 16	Week 20	Week 24	Week 28	Week 32	Week 36	Week 40	Week 44	Week 48	End of Study	Premature discontinuation within 24 weeks	Pre-mature discontinuation post 24 weeks
Clinic Visit(V)/Remote Visit (R)	R1	V2	V3	R4	R5	V6	R7	R8	R9	R10	V11	R12	R13	V14	R15	R16	V17	V17A	R17A		
Timing of visit (weeks)	-12	-3	0	1	2	4	8	12	16	20	24	28	32	36	40	44	48				
Visit window (days)	-84 to -5	-28 to -1		±2	±3	±5	±7	±7	±7	±7	±7	±7	±7	±7	±7	±7	±7	+30			
SUBJECT RELATED INFO/ASSESSMENTS																					
Informed consent	X																				
In/exclusion criteria	X	X																			
Medical history	X																				
Concomitant medication	X	X	X	X		X		X			X			X				X	X	X	
Demographics	X																				
Diabetes history	X																				
Diabetes medication review	X	X	X	X	X	X	X	X	X	X	X	X	X	X	X	X	X	X	X		
Lifestyle Counseling			X	X	X	X	X	X	X	X	X	X	X	X	X	X	X	X	X		
Diabetes education, Handout and instruct in CGM use			X																		
Handout ID card				X																	
Study Exit																		X	X	X	
VITAL SIGNS AND PHYSICAL EXAMINATION																					
Height			X																		
Body weight		X		X		X		X		X		X		X		X		X	X		
BMI		X		X		X		X		X		X		X		X		X	X		
Waist circumference		X						X		X		X		X		X		X	X		
Blood pressure and pulse rate		X	X			X		X		X		X		X		X		X	X		
Physical examination		X																X	X		
LABORATORY TESTINGS																					
Fasting plasma glucose			X			X		X ^[6]			X			X		X		X ^[6]	X		
HbA1c	X	X				X		X		X		X		X		X		X	X		
Fasting insulin		X				X		X ^[6]			X			X		X		X ^[6]	X		

	Screening	Baseline ^[1]	Index Procedure	Week 1	Week 2	Week 4	Week 8	Week 12	Week 16	Week 20	Week 24	Week 28	Week 32	Week 36	Week 40	Week 44	Week 48 End of Study	Premature discontinuation within 24 weeks	Pre-mature discontinuation post 24 weeks
Clinic Visit(V)/Remote Visit (R)	R1	V2	V3	R4	R5	V6	R7	R8	R9	R10	V11	R12	R13	V14	R15	R16	V17	V17A	R17A
Timing of visit (weeks)	-12	-3	0	1	2	4	8	12	16	20	24	28	32	36	40	44	48		
Visit window (days)	-84 to -5	-28 to -1		±2	±3	±5	±7	±7	±7	±7	±7	±7	±7	±7	±7	±7	+30		
Fasting serum C-peptide	X										X								
MMTT (Mixed meal tolerance test)			X					X									X	X	
HOMA-IR			X			X		X			X			X			X	X	
Fasting lipid panel			X								X						X	X	
Metabolic Panel ^[2]	X	X		X				X			X			X			X	X	
Pancreatic Enzyme (Lipase, Amylase)		X		X															
Serum Iron, transferrin, saturation, ferritin, serum folate, Vitamin D, Vitamin B12			X								X						X	X	
CBC with differential	X	X		X		X		X			X			X			X	X	
Serum Glutamic acid decarboxylase antibody (Anti-GAD)	X																		
H. Pylori test ^[3]	X	X																	
Pregnancy test ^[4]	X	X																	
EKG		X																	
ENDOSCOPIES																			
DMR procedure			X																
Endoscopic follow up							X ^[5]												
SAFETY																			
Hypoglycaemic episodes	X	X	X	X	X	X	X	X	X	X	X	X	X	X	X	X	X	X	X
CGM ^[7]		X	X	X	X	X		X			X			X			X	X	X
Adverse events	X	X	X	X	X	X	X	X	X	X	X	X	X	X	X	X	X	X	X

^[1] Screening and baseline visits may be combined if screening visits or tests falls within baseline visit window.

^[2] Metabolic panel includes albumin, total protein, , ALP (alkaline phosphatase), ALT (alanine transaminase), AST (aspartate aminotransferase), bilirubin, urea, creatinine, eGFR.

^[3] breath or stool test

^[4] For women with child-bearing potential.

^[5] Endoscopic follow-up target window is between Week 2-5.

^[6] Only when MMTT is not performed.^[7] CGM will be used for the duration of the follow up in insulin cohort.

APPENDIX 4. INSULIN COHORT PROTOCOL ADDENDUM

APPENDIX 4. REGENT-1 Study Insulin Cohort Addendum

1. BACKGROUND & RATIONALE

Patients with type 2 diabetes (T2D) are initially treated with non-insulin glucose-lowering medications. Due to the progressive nature of T2D, insulin therapy is often needed late in the course of disease. Insulin therapy typically starts with basal insulin. When basal insulin is insufficient in achieving patient's glycemic target, addition of bolus insulin or other medications will be initiated. Insulin therapy is associated with significant shortcomings includinSg its injectable delivery mode, weight gain, propensity of hypoglycemia and an increased need for a comprehensive diabetes management.

The REGENT-1 study is designed to assess the feasibility and preliminary safety of the Endogenex device for endoscopic duodenal mucosal regeneration in patients with type 2 diabetes (T2D). The original protocol included patients with T2D inadequately controlled on non-insulin glucose-lowering medications. However, using the duodenal mucosal regeneration (DMR) therapy in patients inadequately controlled on insulin with a treatment goal of stopping insulin represents a clinically attractive approach. van Baar et al. has demonstrated the concept by using a thermal balloon ablation technique in 16 patients who had inadequate glycemic control while on long-acting insulin at baseline.¹ Post DMR procedure, 69% of patients were off insulin at 6 months while maintaining HbA1c target of 7.5% and 53% remained off insulin at 18 months.

2. DEVICE DESCRIPTION

The investigational device description is provided in the main protocol.

3. OBJECTIVES AND ENDPOINTS

The primary objective of the IS Cohort is to assess the feasibility and preliminary safety of the Endogenex device for endoscopic duodenal mucosal regeneration in individuals with T2D on insulin therapy.

The study will also assess, as exploratory endpoints, treatment efficacy, evaluated by changes in or maintenance of glycemic control in the absence of exogenous insulin therapy. **Table 1** below outlines the study objectives and endpoints. NIS Cohort is described in the main study protocol but listed here for reference.

Table 1. Study Objectives and Endpoints

Objectives	Endpoints	
	NIS Cohort	IS Cohort
Primary		
• To assess the safety of the Endogenex device for DMR procedure	• Proportion of participants experiencing one or more device- or procedure-related serious adverse events at 3 months post procedure.	
Secondary		
• To assess the technical feasibility of the Endogenex device for DMR procedure	• Procedure success: defined as successful treatment of at least 6 cm of duodenum segment. • Procedure time: defined as the time between the Endogenex catheter insertion and the catheter removal.	
• To assess changes in glycemic control	• Change from baseline in glycemic parameters post index procedure, by visits 
○ HbA1c○ Fasting plasma glucose (FPG)○ Insulin-resistance by HOMA-IR○ Post prandial plasma glucose (PPG), Beta cell function, disposition index by mixed meal tolerance test (MMTT) • Change in glucose-lowering medication usage	• Proportion of treated participants with an HbA1c improvement of 0.3% or more at 24 weeks from baseline • Proportion of treated participants with an HbA1c improvement of 0.3% or more at 24 weeks from baseline and maintained at 48 weeks

		of insulin at 24 weeks and maintained at 48 weeks

 To assess liver enzymes and other metabolic changes 	
 Change in liver enzyme from baseline at 24 weeks 
 Alanine Aminotransferase (ALT) Aspartate Aminotransferase (AST) Change from baseline in blood pressure and lipid profile by visit Change in weight from baseline by visit 	

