7.8 Mixed Meal Tolerance Test

Following a minimum of 8-hour fast, the participant will undergo an MMTT which involves the consumption of a standardized mixed meal, consisting of 200ml of Ensure Plus and an Optifast bar with a combined calorie of 533 Cal (carbohydrate 63.4g, protein 31.8g, fat 17.4g, Fiber 6.7g) , and collection of timed serial blood samples for measurement of plasma glucose, insulin and C-peptide through 180 minutes after consumption of the standardized meal (with no additional food intake during this time).

The MMTT should be started between 7AM and 11AM. A cannula is placed in a forearm vein. The standardized meal will be consumed within 5 minutes, and the blood samples will be collected within 15 minutes before consuming the standardized meal (ie, “0 minutes”), and at 10, 20, 30, 60, 90, 120, and 180

minutes after consumption. Blood sampling should occur as close as possible to the specified times (± 5 minutes) for the MMTT.

The MMTT will be performed at the time points specified in the SoA (Appendix 2). The test requires the participant to visit to the testing laboratory. If the risk of potential COVID-19 exposure outweighs the benefit of performing the test in the opinion of the Investigator, the investigator may decide not to perform this test but perform tests for HbA1c, FPG and insulin instead. Follow-up MMTT will only be scheduled in participants who had baseline MMTT data.

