7.12.6 Premature Discontinuation

If a participant discontinues the study prematurely prior to his/her 24-week visit, to the extent possible, the participant should be scheduled for an onsite visit (V17A on SoA, Appendix 2), and the following assessments/procedures should be performed.

- Body weight, calculation of BMI, waist circumference
- Vital signs
- Concomitant medications
- Assessment of AEs that occurred since the last visit
- Hematology (CBC)
- Glycemic parameters (FPG, HbA1C, fasting insulin, HOMA-IR, MMTT)
- Comprehensive metabolic panel
- Fasting lipid panel
- Serum iron, transferrin, saturation, ferritin, serum folate, Vitamin D, Vitamin B12
- CGM data
- Diabetes and medication review by treating physician
- Lifestyle modification counseling
- Study exit

If premature discontinuation is decided during a scheduled visit, the visit will be converted to a V17A and assessment procedures should be performed accordingly.

If a participant discontinues the study prematurely after his/her 24-week visit, a remote visit (R17A) should be scheduled. The following tasks will be performed.

- Concomitant medications
- Assessment of AEs that occurred since the last visit
- CGM data, if available
- Study exit

The primary reason for premature study discontinuation must be documented on the eCRF.

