4. STUDY DESIGN

The IS Cohort will enroll 20 participants initially and up to 30 participants with T2D on basal insulin therapy. Patients who sign the informed consent and are deemed eligible following a general and endoscopic screening will be enrolled in the study.

The index procedure and periprocedural care is described in the main protocol.

The background glucose-lowering medications at baseline and during follow up for each cohort are shown in **Figure 1**.

Eligible participants will be on long-acting insulin with or without short- or rapid acting insulin (up to 60 IU/day and no more than 30% of short/rapid acting components) with or without up to four stable dose of non-insulin glucose lowering medications for at least 3 weeks at baseline.

Post procedure, non-insulin background medications will be resumed to the baseline dose and maintained during the follow-up phase. Insulin dose will be titrated based on fasting glucose levels and may be discontinued if the daily insulin dose is reduced to 10 IU or 0.1 IU/kg and fasting glucose level is at target.

Participants will receive lifestyle-modification counseling sessions at scheduled intervals to promote adherence to a diet and lifestyle suitable for individuals with diabetes. Counseling will be provided by a member of the research team (endocrinologist, dietitian, nurse, etc.) trained in the delivery of lifestyle counseling for diabetes.

Participants will undergo the same follow up schedule, study procedures and data collection as those described in the main study protocol.

[figure not shown]

Figure 1. Insulin Cohort Design

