6.1.1.3. Allowed pre-mixed insulin includes

- NovoMix® 30 (30% rapid, 70% intermediate Protaphane)
- Humalog® Mix 25 (25% rapid, 75% intermediate Humulin NPH)
- Ryzodeg 70:30 (70% long acting Degludec, 30% rapid Aspart)
- Mixtard® 30/70 (30% short, 70% intermediate Protaphane)
- Humulin® 30/70 (30% short, 70% intermediate Humulin NPH).

For the index procedure, participants will be instructed to fast overnight. A general recommendation is to administer 50% of their typical insulin dose at their usual time typically the preceding evening or the morning of the procedure day. However, the investigator should individualize insulin management for each subject particularly if S/RA is a component of their insulin regime.

- Following the procedure, participant's baseline insulin dose will be reduced to avoid hypoglycemia in the setting of a reduced caloric intake post procedure. Subsequently the insulin dose will be titrated to achieve a fasting glucose target of 5.0 – 7.2 mmol/L. Specifically, the following algorithm will be instituted.
- Continue insulin at 50% of the baseline dose on day 1 post procedure.
- Increase insulin dose by 2 units or 10% (as per recommendation of the treating investigator or provider) if fasting glucose is above the target of 7.2 mmol/L over 3 consecutive days.
- Alternatively, reduce insulin dose by 2 units or 10% (as per recommendation of the treating investigator or provider) for a single morning blood glucose or CGM reading less 5.0 mmol/>, or any episode of symptomatic hypoglycemia.
- If daily insulin dose is reduced to 10 units or 0.1 units/kg and fasting glucose is within the target range, insulin may be discontinued with close follow up of glycemia through CGM.
- If insulin is not completely withdrawn by 24 weeks, the background therapy may be intensified to further decrease or eliminate reliance on exogenous insulin. Intensification of background therapy may include addition of a GLP-1a, or an SGLT2i if the participant is already taking or has demonstrated an intolerance to GLP-1a. The insulin titration following intensification of background glycemic therapy should follow the same algorithm as described above.

The above algorithm is provided as a guideline. Investigator should apply clinical judgement to individualize therapy including insulin dosing and background glycemic medications.

Participants in the IS cohort should be instructed to use CGM to monitor his/her glucose levels throughout the duration of the study.

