7. STUDY EVALUATION AND STUDY VISITS

Participants will have the same study evaluations and follow up schedule as in NIS Cohort described in the main study protocol. Points specific to IS Cohort participants are described below.

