7.2. Baseline Visit

Individuals who meet the screening eligibility criteria will be scheduled for baseline visit. The baseline visit will be conducted within 4 weeks from the index procedure. If a screening consent was used at the screening visit, the full study consent must be obtained at this visit. .

Participants who no longer meeting the eligibility criteria at the baseline visit will be considered screen failure and exit the study.

For fasting blood sample collection at the baseline visit, participants will be instructed have the blood sample collected in the morning after an overnight fasting (>8 hr) and to skip their daily insulin dose the evening prior to blood collection. After the blood collection, participant will administer a third (1/3) of their daily insulin dose.

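### In the insulin cohort, HOMA-IR based on fasting insulin can rise or fall with the injected dose and the sampling conditions, with no change in insulin resistance

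*Protocol*

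**What the plan says.** Appendix 4, section 3 (Table 1) places "Insulin-resistance by HOMA-IR" among the glycemic parameters summarised as change from baseline by visit. The table is broken in the extracted text, but Appendix 4, section 7 settles that the measure applies to the IS cohort: "Participants will have the same study evaluations and follow up schedule as in NIS Cohort described in the main study protocol". The main Schedule of Activities puts HOMA-IR at baseline and Weeks 4, 12, 24, 36 and 48. The main protocol gives no formula. It lists the measure beside fasting insulin, for example in section 7.12.6: "Glycemic parameters (FPG, HbA1C, fasting insulin, HOMA-IR, MMTT".

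IS participants enter on injected insulin, "up to 60 IU/day and no more than 30% of short/rapid acting components" (Appendix 4, section 4). Appendix 4, section 6.1.1.3 then changes that dose: "Continue insulin at 50% of the baseline dose on day 1 post procedure", followed by titration to fasting glucose. It goes on: "If daily insulin dose is reduced to 10 units or 0.1 units/kg and fasting glucose is within the target range, insulin may be discontinued".

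The insulin condition at blood sampling differs by visit:
- Screening (Appendix 4, section 7.1): one third of the daily dose is given the evening before.
- Baseline (Appendix 4, section 7.2): participants "skip their daily insulin dose the evening prior to blood collection".
- Follow-up: there is no IS-specific rule. Main protocol section 7.7 asks only that diabetes medication be held on the morning of the visit.

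C-peptide is collected. Section 7.8 provides for "collection of timed serial blood samples for measurement of plasma glucose, insulin and C-peptide through 180 minutes", with the test at baseline and Weeks 12 and 48, and the Schedule of Activities adds a fasting C-peptide at Week 24. Neither is linked to HOMA-IR. Appendix 4, section 11 has efficacy analysed by cohort under the main protocol's descriptive methods. It gives no adjustment for insulin dose and no assay specification.

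**The concern.** HOMA-IR is proportional to fasting glucose times fasting insulin, and it is read as resistance on the footing that the insulin is the participant's own. Participants who inject break that footing to whatever extent the assay detects the injected product. The protocol also acts on both factors: injected insulin is what is adjusted, and fasting glucose is the target it is adjusted to.

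A second problem comes from sampling. The baseline sample follows a skipped evening dose, while a follow-up sample may not. A participant still injecting in the evening could show more measured insulin at follow-up than at baseline, even on a lower dose.

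A report that follows the plan as written could therefore present a change in HOMA-IR as a change in insulin resistance when some or all of it comes from dose and sampling.

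**Working it through.** The documents give no HOMA-IR formula, effect size, standard deviation or expected change, so there is no planned figure to reproduce. What follows is an illustration.

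**Inputs from the documents.** The dose goes to half the baseline dose on day 1 and may later be stopped (Appendix 4, 6.1.1.3). The evening dose is skipped before the baseline sample (Appendix 4, 7.2). Only a morning hold applies at follow-up (main protocol, 7.7).

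**Assumptions not in the documents.**
- HOMA-IR is fasting glucose × fasting insulin ÷ a constant. The constant cancels in a percent change.
- Fasting glucose and the participant's own insulin do not change.
- s is the share of measured fasting insulin that is injected at the full usual dose: 0.1, 0.3 or 0.5. The assay detects it.
- d is follow-up dose ÷ baseline dose: 0.5 (halved) or 0 (withdrawn).
- r is the share of the injected component still measured at sampling: 1 if no dose is skipped; 0, 0.25 or 0.5 after a skipped evening dose.

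**Formula.** Percent change = [(1 − s) + s·d·r_followup] ÷ [(1 − s) + s·r_baseline] − 1.

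**Worked cases.**
- Matched sampling, no skip, s = 0.5, withdrawn: 0.5 ÷ 1 − 1 = −50%.
- Skipped at baseline only, s = 0.5, r_baseline = 0.5, withdrawn: 0.5 ÷ (0.5 + 0.25) − 1 = −33.3%.
- Skipped at baseline only, s = 0.5, r_baseline = 0, half dose: (0.5 + 0.25) ÷ 0.5 − 1 = +50%.
- Skipped at baseline only, s = 0.5, r_baseline = 0.5, half dose: 0.75 ÷ 0.75 − 1 = 0%.

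**Results.**

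| Sampling | Dose | s = 0.1 | s = 0.3 | s = 0.5 |
|---|---|---|---|---|
| No skip at either visit | half | −5% | −15% | −25% |
| No skip at either visit | withdrawn | −10% | −30% | −50% |
| Skipped at both, r = 0.25 to 0.5 | half | −1.4% to −2.6% | −4.8% to −8.8% | −10.0% to −16.7% |
| Skipped at both, r = 0.25 to 0.5 | withdrawn | −2.7% to −5.3% | −9.7% to −17.6% | −20.0% to −33.3% |
| Skipped at baseline only, r = 0 to 0.5 | half | +5.6% to 0% | +21.4% to 0% | +50% to 0% |
| Skipped at baseline only, r = 0 to 0.5 | withdrawn | 0% to −5.3% | 0% to −17.6% | 0% to −33.3% |

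The last two rows are closest to the plan as written for a participant who injects in the evening. They also show that the sign depends on whether the participant is still injecting at follow-up.

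**The case against.** The strongest reply is that the protocol already limits the problem. The skipped evening dose takes injected insulin out of the baseline sample, and the morning hold does some of the same at follow-up. If little injected insulin remains, or the assay does not detect it, the withdrawal artefact is near zero. This is right as far as it goes. It does not close the point, because Appendix 4, section 6.1.1.1 allows long-acting and twice-daily insulins, and nothing in the documents shows that one skipped evening dose clears them. The follow-up rule also does not mention the preceding evening.

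A second reply is that the illustration fixes too much. If resistance is truly unchanged, removing injected insulin should raise glucose or the participant's own insulin, which offsets the fall. That also stands. The falls in the table are therefore better read as the upper end for a given s. To cancel the 30% fall at s = 0.3 fully, own insulin would have to rise from 0.7 to 1.0, that is by 43%.

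Some stronger readings are tempting but not supported:
- A reader might infer that the artefact is always a fall. The unmatched sampling rules allow a rise as well.
- A reader might infer that HOMA-IR is offered here as evidence of mechanism. Appendix 4 lists it under glycemic control and calls efficacy exploratory.
- A reader might infer that a comparison with the non-insulin cohort is compromised. None is planned, since efficacy is analysed by cohort.

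**Conclusion.** The concern holds in a limited form. In the IS cohort, change in insulin-based HOMA-IR mixes any change in resistance with the protocol-driven change in injected insulin and with different sampling conditions at baseline and follow-up. The bias can go either way.

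Its size cannot be known from the documents. The spread of −50% to +50% across the cases shown depends on an assumed injected share of 10-50%, assumed carry-over after a skipped dose, an assay that detects the injected product, and fixed glucose and own insulin. It marks what is possible and is not an estimate.

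The consequence is modest. This is one descriptive secondary endpoint in a single-arm feasibility cohort of 20, up to 30, participants. No test, sample size or safety conclusion rests on it. It is still worth correcting, because the C-peptide samples for a better measure are already scheduled.

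**What to change.** Make the change in Appendix 4. The supplied SAP describes 20 patients on non-insulin agents and does not cover this cohort.

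1. For the IS cohort, specify a C-peptide-based resistance index, with its formula, as the reported measure. Use the time-0 C-peptide of the mixed meal test at baseline and Weeks 12 and 48, and the fasting C-peptide at Week 24.
2. If insulin-based HOMA-IR is shown at all, present it by insulin status and dose at each visit, labelled as not interpretable as resistance while the participant is on insulin. Restricting it to pairs of samples both taken off insulin would leave almost nothing, because every IS participant is on insulin at entry.
3. Reconcile main protocol section 7.7 with Appendix 4, sections 7.1 and 7.2, so that the sampling condition for IS follow-up visits is stated. Which condition applies is a clinical matter for the sponsor and investigators.

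The analysis change costs wording only, but it has three drawbacks:
- There are fewer time points: Weeks 4 and 36 have no C-peptide.
- The meal test may be omitted at the investigator's discretion, and section 7.8 then substitutes HbA1c, fasting glucose and insulin, without C-peptide.
- C-peptide itself responds to injected insulin. Appendix 4, section 7.1 acknowledges this by setting the evening dose with C-peptide measurement in mind. The index avoids counting injected insulin as the participant's own, but it does not remove all dependence on dose, so item 3 matters for it too.
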